This study is a single-masked, two-group, randomized trial to test the effectiveness of CAPABLE in reducing ADL difficulties compared to those randomized to usual care. The experimental group will receive CAPABLE services, which include visits from an Occupational Therapist, a Registered Nurse, and a licensed Handyman. The usual care group will not receive additional visits from study clinicians. All participants will be interviewed at 20 and 52 weeks post-baseline. Re-admission to skilled home health care, acute care hospitalization, skilled nursing facility, and nursing home admission will be assessed via VNSNY CHOICE claims data at 90 days (33 weeks) post follow up assessment. We will evaluate overall health care costs at 52 weeks (long-term impact). Outcome measures will be assessed by interviewers and analysts masked to treatment assignment and without interventionist contact.

STUDY PROTOCOL

A. Purpose and Specific Aims

The overall goal of this rigorous experimental study is to test the effectiveness of a multi-component homebased intervention to enhance physical function of patients who have ADL difficulties and have been recently hospitalized. We will conduct a pragmatic effectiveness trial in the skilled home health setting to evaluate CAPABLE in approx. 268 racially and ethnically diverse older adults with ADL difficulties following hospitalization and skilled home health care.

Primary Aim:

Hypothesis: those receiving CAPABLE will have fewer ADL difficulties

- 1) Test the effectiveness of CAPABLE in reducing the number of ADLs performed with difficulty at 20 weeks post-randomization
- 2) Estimate CAPABLE's economic impact on subsequent health care utilization and costs over 52 weeks post-randomization compared to CAPABLE program cost.

Secondary Aim:

- 1) Testing CAPABLE effectiveness on ADL function at 52 weeks
- 2) Testing effects for key subgroups (gender, ethnicity)
- 3) Examining theoretically-driven mediation pathways for treatment mechanisms

B. Background

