E1. Analytic Approach. The overall goal of this rigorous experimental study is to test the effectiveness of a multi-component homebased intervention to enhance physical function of patients who have ADL difficulties and been recently hospitalized. We will use intention-to-treat analysis (ITT) as the primary method to analyze the results; data from all participants will be analyzed as members of their assigned study group. We may analyze post randomization data (e.g., treatment compliance) in supplementary analyses, such as complier-average causal effect (CACE) models. In addition to the primary outcome, numerous comparisons will be conducted for the secondary outcomes. P-values from these secondary outcomes will be considered descriptive indicators of the intervention impact, and not as absolute indicators for null hypothesis testing, which might require p-value adjustments for inflated type I error rate due to multiple comparisons. For our primary analyses, we will use cases with complete data. We will also conduct sensitivity analyses comparing the complete case analysis with analyses that use multiple imputation for missing data. Models will compare imputation done 1) for all people with missing data, including deceased cases, and 2) for only those who survived but dropped out.

E2. Sample Size

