- 1) Test the effectiveness of CAPABLE for reducing ADL difficulties compared to usual care baseline to 52 weeks.** Additional, multilevel longitudinal analyses will incorporate the 52-week outcome data to examine the maintenance of any intervention effects. In these models, time since randomization (20 vs. 52 weeks) will be examined as a within-person or repeated measures factor, and group*time interaction tests will determine whether there are different trajectories of change in ADL (primary outcome) and the other continuous secondary outcomes (IADL, depressive symptoms).
- 2) Explore whether the intervention has differential effectiveness across subgroups.** We will explore subgroup effects and heterogeneity of intervention response. Key subgroups will include those defined by gender, ethnicity, living arrangement, (e.g., with vs. without a co-residing caregiver), type of hospitalization (e.g., surgical vs. nonsurgical) and medical complexity (e.g., high vs. low Charlson comorbidity scores). We will add interaction terms to the models to test empirically whether the intervention is more or less effective in one group compared to a reference group, and examine stratified analyses where we observe significant interaction effects.
- 3) Examine theoretically-driven mediation pathways to identify potential mechanisms of intervention effectiveness.** We hypothesize multiple intermediate variables as possible mediators of the intervention's impact including changes in depression, pain, and control strategy use. For each of these

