proposed mediators, we will use models specifically developed for testing mediation effects in two-wave intervention trials and applied by our team for continuous outcome variables and for event outcomes. We will use structural equation modeling with baseline-adjusted changes in potential mediators regressed on the intervention condition to determine one leg of the mediation effect (a path) and baseline-adjusted changes in primary and secondary outcome variables regressed on changes in the mediator to estimate the second leg of the mediation effect (b path). The remaining adjusted intervention effect on the outcome variable represents the direct or unmediated effect (c' path). Mplus software calculates standard errors for mediation effect (a*b) using the Sobel or delta method and bootstrapping methods are also available to test the significance of the mediated effect. We will interpret and quantify significant mediation pathways to identify important intervention mechanisms. Furthermore, the proportion of the total intervention effect that can be attributed to any particular mediator will be calculated by $(a*b)/((a*b)+c')$. Multiple group structural equation models and associated nested comparisons of constrained and unconstrained models will also be employed to examine if mediation effects differ significantly by the subgroups listed above (secondary aim 4). Collectively, the analyses in secondary aim 4 will identify the pathways by which the intervention is delivering intended effects on outcomes and the patient subgroups that are particularly likely to benefit via specific pathways.

We have elected to not consider interim analyses in this study due to the extended time for recruitment and the low likelihood of a sufficiently large effect that would make it possible to stop early. However, we will revisit this decision with the DSMB at its first organizational meeting.

F. Risks

F1. Risks and Benefits to participants

- i. **Potential Risks:** The study intervention does not pose risks greater in and of themselves than those ordinarily encountered in daily life or during the performance of routine physical or psychological examinations or tests. However, this study involves exercise and discussion of changes of medication regimens with primary care providers. The potential risks to study participants include falls from increased exercise or participant changing own medication regimen after discussion of medications.

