The overall goal of this rigorous experimental study is to test the effectiveness of a multi-component home-based intervention to enhance physical function of patients who have ADL difficulties and have been recently hospitalized compared to a usual care control group. We will use an intention-to-treat (ITT) analysis to compare these two conditions; data from all participants will be analyzed as members of their randomly assigned treatment group. The primary outcome will be the Katz measure of difficulties with activities of daily living (ADLs). Scores on this measure range from 0 to 16, with higher scores indicating greater disability. In addition to the primary outcome, several additional comparisons will be conducted on secondary outcome variables. Because there is only one primary outcome measure, no adjustment for type I error is made for multiple comparisons, and a statistically significant finding will be indicated if the p-value is less than 0.05 for the treatment effect. This would indicate a type I error rate of less than 5% for rejecting the null hypothesis of no difference between treatment groups if the null hypothesis is, in fact, true. Two-tailed tests will be used for all statistical comparisons. P-values will also be reported for the secondary outcome analyses but these p-values from the secondary analyses will be considered descriptive indicators of the intervention impact on those measures and not as absolute indicators for null hypothesis testing.

Comparison Group Selection

This is a two group comparison. A total of 268 participants will be enrolled and randomized in a 1 to 1 ratio to either the intervention condition or to a usual care control group, with 200 participants expected to provide outcome data after accounting for 25% attrition. A total of 200 participants for analysis will provide 80% power to detect a clinically meaningful difference of 0.40 standard deviation units between intervention and usual care groups on the primary outcome measure of ADL difficulty.

Type of Statistical Test

This two group comparison will be a test of **superiority**. A two-tailed test will be used with the type I error rate set at 0.05.

Statistical Test of Hypothesis (Primary Outcome)

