The **method** to be used to calculate the p-value given the null hypothesis of no difference between the two treatment groups is an analysis of covariance (ANCOVA). The outcome variable will be the 20-week Katz summary disability score. Treatment group (intervention vs. usual care control) will be the primary independent variable. The baseline (pre-treatment) Katz summary disability score will be the primary covariate. Other baseline demographic (e.g., gender), functional ability, and clinical variables (e.g., Charlson comorbidity index, pre-hospitalization ADL function) may be included as additional covariates if there are any random imbalances on those variables across intervention groups or if they are significantly correlated with the 20-week Katz score after adjustment for the baseline Katz score.

Method of Estimation (Primary Outcome)

An ordinary least squares estimate of the mean difference, adjusted for covariates, will be used. Consistent with the pre-specified type I error rate of 0.05, 95% confidence intervals will be reported for this covariate-adjusted mean difference.

Parameter Dispersion Type (Primary Outcome)

The standard error of the mean will be used to characterize dispersion and to calculate the 95% confidence interval.

Statistical Tests of Hypotheses (Secondary Outcomes)

Secondary outcomes include discrete events such as hospitalization and admission to skilled home health care, skilled nursing facility, and nursing home. Time to event (i.e., survival analysis) models will be used to examine intervention impact on these discrete outcomes. Cox regression (proportional hazards) models will be conducted with intervention group as the primary predictor variable and baseline demographic (e.g., gender), functional ability, and clinical variables (e.g., Charlson comorbidity index, pre-hospitalization ADL function) included as covariates.

Method of Estimation (Secondary Outcomes)

Hazard ratios (with usual care as the reference group) will determine the degree to which the intervention was effective in reducing the rates of (or delaying) these discrete event outcomes. All hazard ratios will be accompanied with 95% confidence intervals to aid interpretation and to characterize potential variability of the true intervention effect.

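### Secondary Aim 1 asks about effectiveness at 52 weeks, but the only test named for it, group by time over 20 and 52 weeks, measures change in the effect between those visits

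*Combined protocol and SAP*

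**What the plan says.** Protocol section A lists the first secondary aim as "Testing CAPABLE effectiveness on ADL function at 52 weeks". The heading of E4, aim 1 puts it as "Test the effectiveness of CAPABLE for reducing ADL difficulties compared to usual care baseline to 52 weeks". Both ask how CAPABLE compares with usual care at one year.

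The method under that heading is described this way: "multilevel longitudinal analyses will incorporate the 52-week outcome data to examine the maintenance of any intervention effects". It then states that "time since randomization (20 vs. 52 weeks) will be examined as a within-person or repeated measures factor, and group*time interaction tests" will show whether ADL trajectories differ, and applies the same approach to IADL and depressive symptoms. No group difference at 52 weeks, and no group main effect, is named.

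The rest of the plan does not supply one:

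- The ANCOVA in E3, aim 1 and in the SAP (Statistical Test of Hypothesis, Primary Outcome) is for the 20-week Katz score.
- The SAP section on secondary outcomes opens with "Secondary outcomes include discrete events such as hospitalization and admission to skilled home health care" and describes only time-to-event models.
- The mediation models in E4, aim 3 contain treatment paths ("baseline-adjusted changes in potential mediators regressed on the intervention condition"), but they serve to study mechanisms and do not designate a 52-week treatment effect.

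On the status of secondary results, E1 says "P-values from these secondary outcomes will be considered descriptive indicators of the intervention impact", and the SAP overview says "these p-values from the secondary analyses will be considered descriptive indicators".

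**The concern.** The named test answers a different question from the aim. An interaction over two post-baseline visits asks whether the treatment effect changed between them. The aim asks whether there is an effect at the second visit.

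The two can point in opposite directions. If the whole 20-week benefit is still there at 52 weeks, the aim's answer is yes and the interaction is null. If the benefit has gone by 52 weeks, the aim's answer is no and the interaction will usually be significant. A non-significant interaction does not show maintenance either: it also arises when there was no effect at either visit, or when the change was too small to detect.

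At stake is the durability result. The estimate and confidence interval that would answer it are not designated, so the choice is left until the data are in hand. The same gap affects IADL and depressive symptoms. Outside the mediation models, this interaction is the only analysis designated for the treatment effect on them.

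**Working it through.** **1. The plan's own figure.** E2 gives 134 enrolled per arm for 0.40 SD, 80% power, two-sided 0.05 and 25% attrition. A two-sample t-test needs 100 per arm, and 100/(1 − 0.25) = 133.3, rounded up to 134. This reproduces exactly. It concerns 20 weeks; no power is stated for the 52-week aim.

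**2. What the interaction estimates.** Let d20 and d52 be the group differences at the two visits, in SD units. With time at 20 and 52 weeks only,

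interaction = d52 − d20.

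If d52 = d20 the interaction is zero whatever the size of the effect, so the test rejects at its nominal 5%. This step needs no assumption about correlation or retention.

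**3. Assumptions for the remaining figures.** The documents give neither 52-week attrition nor correlations, so these are assumed:

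- n = 90 per arm with 52-week data (about 33% loss: 134 × 0.67 = 89.8), range 80 to 100
- correlation rho between the 20- and 52-week scores: 0.4 to 0.8
- correlation r between baseline and the 52-week score: 0.4 to 0.6 (0 for the unadjusted contrast)
- d20 = 0.40 SD, the difference E2 is sized to detect

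All powers use the noncentral t distribution, two-sided 0.05.

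**4. Interaction.** SE = √(2(1 − rho)) × √(2/n). For n = 90 and rho = 0.4: √1.2 × √(2/90) = 1.095 × 0.149 = 0.163.

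| n = 90 per arm | rho 0.4 | rho 0.6 | rho 0.8 |
|---|---|---|---|
| SE | 0.163 | 0.133 | 0.094 |
| Effect kept (0.40 to 0.40) | 5% | 5% | 5% |
| Effect halved (0.40 to 0.20) | 23% | 32% | 56% |
| Effect lost (0.40 to 0) | 68% | 85% | 99% |

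Over 80 to 100 per arm, the halved-effect range widens to 21% to 61% and the lost-effect range to 63% to 99%.

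**5. Direct 52-week contrast.** SE = √(1 − r²) × √(2/n). For n = 90 and r = 0.5: 0.866 × 0.149 = 0.129. Power when d52 = 0.40:

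| n per arm | Unadjusted | r = 0.4 | r = 0.5 | r = 0.6 |
|---|---|---|---|---|
| 80 | 71% | 78% | 83% | 88% |
| 90 | 76% | 83% | 87% | 92% |
| 100 | 80% | 87% | 90% | 94% |

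If the effect is lost (d52 = 0), this contrast rejects 5% of the time.

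**6. Simulation check.** With 90 per arm and 8,000 trials per setting, the 52-week score and the 52-minus-20-week difference were each regressed on group and baseline, at (r, rho) = (0.4, 0.4), (0.5, 0.6) and (0.6, 0.8).

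- Effect kept: contrast 83%, 87%, 92%; interaction 5% throughout.
- Effect halved: interaction 23%, 33%, 55%.
- Effect lost: contrast 5% throughout; interaction 67%, 85%, 99%.

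These agree with the formulas.

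**The case against.** The strongest reply is that the model is sound and only one contrast is unnamed. A longitudinal model with group, time and their interaction yields the 52-week difference directly. That is true, and the model is not criticised. But the text does not say which quantity from it answers the aim. With 20 weeks as the reference level, the group coefficient is the 20-week effect; under sum coding it is the average over both visits.

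A second reply is that E4 presents these models as additional and directed at maintenance. Asking whether an effect already tested at 20 weeks later changes is a coherent use of the interaction. This stands as far as it goes, and the sign of the interaction does show fading or growth. It still does not cover the aim as worded in section A and in the E4 heading. The plan nowhere says that a non-significant interaction will be read as maintenance, so a sentence ruling that out is a safeguard rather than a correction.

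Third, the heading's reference to baseline could suggest that baseline is a level of time, which would make the 52-week term an effect on change from baseline. The parenthesis fixes the levels as 20 and 52 weeks, so the text would have to change for that reading too.

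Fourth, E1 and the SAP overview promise comparisons on secondary outcomes in general, and the SAP's list of discrete events is not worded as exhaustive. Between-group comparisons of IADL and depressive symptoms may therefore be intended, but no model or time point is given for them.

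Finally, the power figures rest on assumed retention and correlations, and two places (the opening summary and C7) describe the 52-week interview as only possible. Fewer completers would lower the power of the direct contrast. The null interaction under a constant effect would be unchanged.

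**Conclusion.** The concern holds. The only test named for Secondary Aim 1 estimates the change in effect from 20 to 52 weeks, and no 52-week ADL contrast is designated anywhere in the protocol or SAP. Under a fully maintained benefit the named test rejects 5% of the time, with no assumption beyond a constant effect. Under the stated assumptions at 90 per arm, the baseline-adjusted 52-week difference would have 83% to 92% power in that case. If half the benefit is lost, the interaction detects it only 23% to 56% of the time, so a non-significant result is weak evidence of maintenance.

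This goes beyond missing detail, because the named test does not answer the stated aim. It should be fixed, but the weight is moderate: the aim is secondary, its p-values are descriptive, and the primary 20-week analysis does not depend on it.

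**What to change.** In E4, aim 1 and in the SAP section on secondary outcomes:

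- Keep the repeated-measures model of the 20- and 52-week scores, with the baseline score as covariate, as in the 20-week ANCOVA.
- Name the adjusted group difference in Katz score at 52 weeks, with its 95% CI, as the analysis of Secondary Aim 1.
- Keep the group-by-time term, with its CI, as a description of change between 20 and 52 weeks, and state that a non-significant interaction will not be read as maintenance.
- For IADL and depressive symptoms, report the adjusted group differences at 20 and 52 weeks with CIs from the same model, as descriptive results.

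The cost is wording only. The data and the model stay the same, a few more contrasts are reported, and the primary analysis is untouched.

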Sample size calculations are based on our ability to detect clinically meaningful effect sizes for CAPABLE on the primary outcome of mean ADL difficulty score. All calculations are based on two-sided tests of 0.05 significance. Assuming a conservative attrition rate of 25% during the 20-week follow-up period, (we have consistently had 13% attrition in prior CAPABLE studies)¹⁰ we would need to enroll 60, 85, and 134 participants per treatment arm to detect, with 80% power, an intervention effect size of 0.60, 0.50, and 0.40, standard deviation units, respectively, at 20 weeks after baseline. Preliminary data showed a 41% reduction in ADL difficulty (*0.76 standard deviation units*) in the post-hospitalized group.¹⁰ Smaller effects of 0.57 to 0.60 standard deviation units were noted for other outcomes, and effect sizes of 0.63 for ADL difficulties and 0.62 for IADL difficulties were obtained in a small RCT pilot.¹⁵ By enrolling at least 268 participants, we anticipate having 20-week outcome data (primary endpoint) on 200 participants after 25% attrition. This sample size will provide excellent power to detect clinically meaningful differences between intervention and usual care groups.

E3. Primary study aims:

- 1. Test the effectiveness of CAPABLE in reducing ADL difficulties compared to usual care after 20 weeks of intervention.** We will address this aim using an analysis of covariance on the 20-week Katz summary disability score with treatment group as the primary independent variable and the baseline Katz score as the primary covariate. Other baseline demographic (e.g., gender) functional ability, and clinical variables (e.g., Charlson comorbidity index, pre-hospitalization ADL function) will be included as covariates if there are any random imbalances on those variables across intervention groups or if they are significantly correlated with the 20-week Katz score after adjustment for the baseline Katz score.

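### Stratified subgroup results are planned where the interaction is significant, with no commitment to report the rest, which favours exaggerated or false subgroup findings (minor)

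*Combined protocol and SAP*

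**What the plan says.** Section A lists among the secondary aims "Testing effects for key subgroups (gender, ethnicity". Section E4, aim 2, widens this to five factors: gender, ethnicity, whether a caregiver lives in the home, surgical or non-surgical admission, and comorbidity burden. Interaction terms are added to the models for these factors, and the team will then "examine stratified analyses where we observe significant interaction effects". The comorbidity factor is described as "medical complexity (e.g., high vs. low Charlson comorbidity scores", with no cut-point. The aim is labelled as exploration.

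Section E4, aim 3, adds multiple-group mediation models over the same subgroups. It closes by saying that these analyses will identify, among other things, "the patient subgroups that are particularly likely to benefit via specific pathways".

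Section E1 and the SAP's Statistical Analysis Overview both treat p-values for secondary outcomes as descriptive. The SAP text does not mention subgroups. Neither document gives a power figure, a significance level or a reporting rule for the interaction tests.

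**The concern.** The only stated trigger for presenting effects within subgroups is a significant interaction. In a trial sized for a main effect, an interaction of moderate size reaches significance only when chance has pushed the estimate upward. The stratified results that get written up are then a selected, inflated set. If the effect is in truth the same for everyone, a false signal can make one group appear to gain nearly everything and the other nearly nothing.

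The background sections justify the trial partly by the need to evaluate CAPABLE in a more ethnically diverse population. A report could follow the plan and still contain no subgroup effect or interaction interval for ethnicity. Using significance as a trigger also sits poorly with the plan's own view that secondary p-values are descriptive.

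Two smaller matters belong here. Splitting Charlson into high and low discards information in a score that is already collected. The closing statement on mediation also promises a finding where an exploration is all that can be offered.

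**Working it through.** **Inputs from the documents.** Section E2: "All calculations are based on two-sided tests of 0.05 significance". Section E2 also states: "we would need to enroll 60, 85, and 134 participants per treatment arm to detect, with 80% power", for effects of 0.60, 0.50 and 0.40 SD with 25% attrition. SAP, Comparison Group Selection: "A total of 200 participants for analysis will provide 80% power to detect a clinically meaningful difference of 0.40 standard deviation units". SAP overview: "Two-tailed tests will be used for all statistical comparisons". Allocation is 1:1.

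**Assumptions, because the documents give no figure.** Interaction tests at 0.05; subgroup share p; baseline-outcome correlation r; true interaction size; Charlson distribution; independence of the five tests.

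**1. The plan's own figures.** Completers per arm = 2(1.960 + 0.842)²/d² = 15.70/d², which gives 44, 63 and 99. Dividing by 0.75 gives 59, 84 and 132. The t-test version needs 45, 64 and 100 completers, or 60, 85.3 and 134 enrolled. The stated 60, 85 and 134 are reproduced. Power with 100 per arm at 0.40 SD is 80% to 81%.

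**2. Interaction precision.** SE = √(1 − r²) × √[(4/N)(1/p + 1/(1 − p))]. With N = 200, p = 0.5 and r = 0, this is √(0.02 × 4) = 0.283 SD. The smallest significant estimate is 1.96 × 0.283 = 0.55 SD.

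**3. Power and exaggeration.** Let λ = true interaction/SE, U = 1 − Φ(1.96 − λ) and L = Φ(−1.96 − λ). Power = U + L. The mean absolute estimate given significance, divided by the truth, is [λU + φ(1.96 − λ) − λL + φ(1.96 + λ)] / [λ(U + L)].

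| Split | r | SE | Power at 0.40 SD | Exaggeration | Power at 0.80 SD | Exaggeration |
|---|---|---|---|---|---|---|
| 50/50 | 0 | 0.283 | 29% | 1.8 | 81% | 1.12 |
| 50/50 | 0.5 | 0.245 | 37% | 1.6 | 90% | 1.06 |
| 50/50 | 0.7 | 0.202 | 51% | 1.4 | 98% | 1.01 |
| 20/80 | 0 | 0.354 | 20% | 2.2 | 62% | 1.27 |

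At 0.60 SD with a 50/50 split, power is 56% to 84% as r goes from 0 to 0.7.

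**4. False signals.** With no heterogeneity, 1 − 0.95⁵ = 0.226. For one such signal (50/50, r = 0), the mean absolute interaction given significance is 0.283 × φ(1.96)/0.025 = 0.283 × 2.34 = 0.66 SD. Around a common true effect of 0.40 SD, the two strata then average 0.40 ± 0.33, that is 0.73 and 0.07 SD. Simulation gave the same values.

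**5. Charlson.** The information kept by a cut is the squared correlation between the cut and the full score. Under assumed Poisson or negative binomial counts with mean 2 to 3, cuts near the median keep about 44% to 67%. Two examples: a negative binomial with mean 3 and size 2, cut at 2 or more, keeps 44%; a Poisson with mean 2, cut at 3 or more, keeps 67%.

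**6. What full reporting would show.** With a 50/50 split and r = 0, each subgroup effect has a 95% CI of ±1.96 × √(4/100) = ±0.39 SD, and each interaction ±0.55 SD. For 80% power at a 0.40 SD interaction, N = 16 × (2.802/0.40)² ≈ 785 analysed participants.

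**The case against.** The strongest reply is that testing an interaction before stratifying is sound practice. It guards against comparing p-values within strata, and the aim is openly exploratory. That stands; the test and the label should both remain.

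Several stronger readings are tempting, and the documents do not support them:

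- A reader might infer that subgroup effects will be withheld unless significant. The plan says when stratified analyses are examined. It is silent on non-significant interactions and does not say that they are suppressed.
- A reader might infer that no effect would be estimated for an ethnic group if its interaction is non-significant. The interaction model yields the effect in the reference group and the difference for the other, whatever the p-value. The multiple-group models in aim 3 are not gated on a significant interaction. What is missing is a reporting commitment.
- A reader might take the Charlson split as fixed. It is an example, and sections E3 and the SAP name the index as a candidate covariate without cutting it.
- A reader might conclude that the plan misses most heterogeneity and overstates whatever it finds. That depends on the size of the interaction, as the 0.60 and 0.80 SD results show.
- A reader might take 23% as the chance that a given significant interaction is false. It is the chance of at least one false signal when none of the five factors matters.
- A reader might want a power figure for mediation differing by subgroup. The documents give no path sizes, so none is offered.

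The statement that p-values are descriptive concerns secondary outcomes and does not expressly cover subgroup tests. The tension is therefore one of principle and not a direct contradiction.

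**Conclusion.** The point holds as a minor one. Presenting stratified results on the strength of a significant interaction, without committing to report the others, favours inflated or false subgroup findings when true interactions are moderate or absent. The size is 29% to 51% power and 1.8 to 1.4 times exaggeration at 0.40 SD, and about a 23% chance of a false signal over five independent null tests. For interactions near 0.80 SD with a balanced split the problem largely disappears.

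These figures rest on assumed subgroup shares, correlations, interaction sizes and independence. An uneven split lowers power, as the 20/80 row shows, and an ethnicity factor with more than two levels would lower it further. The Charlson loss applies only if the example grouping is adopted, and it depends on the assumed count distribution. The primary analysis is unaffected.

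**What to change.** - **Section E4, aim 2, and the SAP:** state that, for every listed factor, the treatment effect in each group and the interaction estimate will be reported with 95% CIs whatever the p-value. Keep the interaction test and the exploratory label. One forest plot can carry the results.
- **Charlson:** enter the baseline score as continuous in the interaction and display the treatment effect at chosen values of the score, fixed in advance.
- **Section E4, aim 3, closing statement:** replace the promise to identify benefiting subgroups with wording that the models will explore whether pathways differ between subgroups.

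The cost is a few sentences and one figure, with no new data, visits or participants. The downside is that wide intervals will be on view. The change removes selective reporting; it does not raise power for the binary factors, and the text should not suggest that it does.
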